Primary Objective	To ensure the use of a swab in SOLO that is comparable to the originally proposed swab for SOLO, determine the preliminary performance characteristics of the new NF swab in a feasibility study.
Primary Endpoints	
 1. A comparison of the proportions of individuals who collect squamocolumnar cells when using a NF swab with a 5 cm vs. a 3 cm insertion depth. 2. A comparison of the proportions of individuals who collect cytologically adequate specimens when using a NF swab with a 5 cm vs. a 3 cm insertion depth. 3. A comparison of the proportions of individuals who collect adequate specimens for molecular genotyping when using the new NF swab vs. the original swab used in the PAC Self-Swab Study. 4. A comparison of the acceptability and pain performance of the new NF swab vs. the original swab and the 5 cm and 3 cm insertion depth.
Pilot Study Design	Two-arm, randomized controlled trial
Eligibility Criteria	Eligibility See section 3.0
Pilot Study Intervention	Swabbing with a new nylon-flocked swab with an insertion depth of 5 cm.

Number of Subjects	60 participants
Estimated Time to Complete Accrual	Approximately 2 months
Subject Participation Duration	Approximately 30 minutes
Estimated Time to Primary Completion	Approximately 4 months
Estimated Time to Pilot Study Completion	Within 6 months of accrual initiation.

LIST OF ABBREVIATIONS

AE	adverse event
CASI	computer-assisted self-interview
HPV	human papillomavirus
IRB	institutional review board
NF	nylon-flocked
PHI	protected health information
PAC	Prevent Anal Cancer
SAE	serious adverse event
SCJ	squamocolumnar junction
SGM	sexual and gender minorities
SOLO	self-sampling to optimize anal lesion outcomes
UPIRSO	unanticipated problem involving risk to subject or other

A Background and Rationale

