The remaining specimen will be delivered to Wisconsin Diagnostic Labs (Milwaukee, Wisconsin) which uses the COBAS 4800 system for cytology reading. Cytology findings will use the Bethesda System³⁹ with classification as follows: negative for intraepithelial lesions; atypical squamous cells of undetermined significance (ASCUS) or atypical squamous cells, cannot rule out high-grade squamous intraepithelial lesion; low-grade squamous intraepithelial lesion; or high-grade squamous intraepithelial lesion. Reflex HPV testing will be conducted for all abnormal (i.e., \geq ASCUS) specimens.

Anal cytology is approved for use in anal cancer screening. Thus, individuals will be given the cytopathology results (either abnormal, normal, or inadequate/unsatisfactory) and any HPV reflex testing results through the individual's preferred mode of communication; however, regardless of the result, all individuals will be encouraged to seek medical advice about their results. Currently, there is no FDA approval for anal self-sampling, thus, the cytology results should not be used to guide care or referrals.

The 0.5 mL aliquot will be batch-shipped to the Moffitt Cancer Center for HPV genotyping. Moffitt will extract DNA from the 0.5 mL aliquot (MDx Media Kit, QIAGEN) and then use the SPH₁₀-LiPA₂₅ kit according to the manufacturer's instructions to first test for adequacy of the specimen, defined by the presence of human RNase P, and second to test for HPV DNA, and HPV genotypes.³⁴

HPV genotyping results from Moffitt will not be available for several months after the cytology screening since the specimens will be batched shipped only after all 60 individuals complete the screening. In addition, participants with abnormal cytology results will also have HPV reflex testing which would indicate if a high-risk HPV type is detected in the cytology specimen. Thus, the results of the HPV genotyping will not be provided to the participant after genotyping is completed and results are available.

F.5 Subject Withdrawal Criteria

F.5.1 Subject-initiated Withdrawal

A participant may decide to withdraw from the study at any time.

F.5.2 Investigator-initiated Withdrawal

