The investigator may withdraw a participant whenever continued participation is no longer in their best interests. Reasons for withdrawing a participant include, but are not limited to, a participant's noncompliance, or simply significant uncertainty on the part of the investigator that continued participation is prudent.

F.5.3 Replacement Policy and Data Usage

[figure not shown]
Individuals who sign the informed consent form and are randomized, but subsequently withdraw, will be replaced. Data collected from individuals that withdraw or discontinue from the study will be used.

F.6 End of Pilot Study Definition

An individual is considered to have completed the study if they have completed the post-cytology survey. Those who participated in the pilot study will not be eligible or involved in the parent SOLO study.

G Pilot Study Team, Assessments, and Procedures

G.1 Pilot Study Team Structure

G.2 Pilot Study Schedule of Events

Procedures and Events	Recruitment	Consent & Cytology Appointment	End of Pilot Study
Eligibility Screening	X		
Informed Consent		X	
Randomization and Enrollment ¹		X	
INTERVENTION			
Self-sampling with a 5 cm nylon-flocked swab		X	
CONTROL			
Self-sampling with a 3 cm nylon-flocked swab		X	
RESEARCH PROCEDURES			
Adverse Events Collection ²	(SAEs only)	AEs collected from the start of the intervention to 30 days after the end of the intervention	
Cytology Appointment Computer-Assisted Self-Interview (CASI) ³			X

¹ After an individual has signed the informed consent form and been randomized to one of the study arms, they are considered enrolled in the study.

² Refer to Section 7.2 for adverse event (AE) collection and reporting requirements.

³ The cytology CASI will be given to participants immediately after they complete cytology collection.

G.3 Pilot Study Procedures to be Conducted by Site

Activity	Milwaukee		Tampa
	Medical College of Wisconsin	Wisconsin Diagnostic Labs	Moffitt Cancer Center
Funding	Primary Award	Service contract	Service contract
Recruitment	X	-	-
Consenting	X	-	-
Randomization	X	-	-
Participant interaction	X	-	-
Obtaining PHI	X	-	-
Surveying	X	-	-
Access to PHI	X	X	-
Supplying cytology kits	X	-	-
Cytology reading	-	X	-
HPV genotyping	-	-	X

Activity	Milwaukee		Tampa
	Medical College of Wisconsin	Wisconsin Diagnostic Labs	Moffitt Cancer Center
Key personnel	X	-	-

H Statistical and Epidemiological Considerations

H.1 Pilot Study Primary Endpoints

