1. A comparison of the proportions of individuals who collect squamocolumnar cells when using a NF swab with a 5 cm vs. a 3 cm insertion depth.
2. A comparison of the proportions of individuals who collect cytologically adequate specimens when using a NF swab with a 5 cm vs. a 3 cm insertion depth.
3. A comparison of the proportions of individuals who collect adequate specimens for molecular genotyping when using the new NF swab vs. the original swab used in the PAC Self-Swab Study.
4. A comparison of the acceptability and pain performance of the new NF swab vs. the original swab.

H.2 Power for Endpoints

This pilot feasibility study does not have the power to make conclusive statements about the study endpoints.

H.3 Analysis Plan

H.3.1 Preliminary analyses

We will assess the success of randomization. For surveys, we will calculate item response rates for each arm of the study and for subgroups based on HIV status, race/ethnicity, and education.⁴³

After evaluating missing survey data, we will use multiple imputation⁴⁴ to maintain the maximum sample size if data are missing at random. Sensitivity analyses will compare results if data are not missing at random.⁴⁵

In each study arm, we will analyze frequencies of survey items, demographics, other domains, adverse events, and serious adverse events.

H.3.2 Primary Endpoint 1

The presence of cells from the squamocolumnar junction will be assessed in each specimen (Yes/No). Proportions of specimens with squamocolumnar cells will be compared for the 5 cm and 3 cm swabs.

H.3.3 Primary Endpoint 2

Cytologic adequacy is defined as the presence of ~2000-3000 nucleated squamous cells. Proportions of adequate specimens will be compared for the 5 cm and 3 cm swabs.

H.3.4 Primary Endpoint 3

The PAC Self-Swab Study molecular adequacy estimates, given study size, were quite precise with narrow confidence limits. The estimates derived from this pilot study will have wider confidence limits. The original and new swabs will be considered to have commensurate molecular adequacy if the exact confidence limits of the original PAC Self-Swab Study swab are covered by the exact confidence limits of the piloted swab.

H.3.5 Primary Endpoint 4

Each participant will receive a short cytology CASI immediately after the cytology screening to rate their acceptability of the cytology screening on a Likert scale and pain on a visual scale.³⁷ Proportions of individuals' ratings for adequacy and pain will be compared for

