The study investigator will be responsible for determining whether an AE is expected or unexpected as indicated in the protocol. An AE will be considered unexpected if the nature, severity, or frequency of the event is not consistent with the risk information previously described for the study intervention.

I.3 Collection and Reporting Requirements for Adverse and Serious Adverse Events

AEs that are Grade 3 or higher and are related (possibly, probably, or definitely) to the intervention will be collected from the time the subject starts the intervention through conclusion of the intervention, which comprises the cytology self-sampling and CASI. AEs will be tracked and followed until resolution, the subject withdraws consent or is lost to follow-up (including individuals who discontinue early). SAEs that occur after the subject has signed the consent form through 30 days after the conclusion of the intervention will be collected. Adverse events collected per the protocol should be followed with appropriate medical management.

AEs will be collected as reported. In the case of an adverse event, participants will be instructed to contact study staff and/or investigators as soon as possible, ideally within 24 hours. All Grade 3 and higher adverse events will be discussed with the PI and appropriate study staff. The PI will oversee that all AEs, SAEs, and UPIRSOs, are reported appropriately. Information about adverse events experienced by study individuals will be monitored by the following means:

- Report given by study participants to study staff, either in person or by telephone.
- Report given to study staff by study participants' family or friends, either in person or by telephone.
- Report by the participant's physician or other health care provider involved in the subject's care.
- Report from a hospital or other healthcare facility where the study participant is being treated for the serious adverse event.
- Other persons who may have knowledge of such a serious adverse event.

The PI will consult with other investigator(s) to assign event attribution category (unrelated, unlikely, possible, probable, or definite).

I.4 Institutional

Adverse and serious adverse events are not expected. If such events occur, AEs and SAEs will be reported per MCW Institutional Review Board (IRB) guidelines and the MCWCC Data and Safety Monitoring Plan (DSMP).

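### SAEs are to be collected for 30 days and tabulated by arm, but no contact to ask about them is scheduled after the visit, so a zero could not be read as zero among all randomised

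*Combined protocol and SAP*

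**What the plan says.** On the window, I.3 states: "SAEs that occur after the subject has signed the consent form through 30 days after the conclusion of the intervention will be collected". On the analysis, H.3.1 states: "In each study arm, we will analyze frequencies of survey items, demographics, other domains, adverse events, and serious adverse events". It names no denominator.

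On how events are found, I.3 states: "AEs will be collected as reported". If an event occurs, "participants will be instructed to contact study staff and/or investigators as soon as possible, ideally within 24 hours". The routes that I.3 then lists are all incoming: the participant, family or friends, a treating clinician, a hospital, or anyone else who knows of the event. I.1.1 adds that an AE may also come to light through an open question from staff, by observation or on examination. It gives no time point, form or script.

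On contact with participants, the protocol summary gives the length of participation as "Approximately 30 minutes". The last item in the schedule of events (G.2) is the survey. It stands in the end-of-study column, but its footnote places it on the day of the swab: "The cytology CASI will be given to participants immediately after they complete cytology collection". F.6 adds: "An individual is considered to have completed the study if they have completed the post-cytology survey". There is one later contact. Under F.4, "individuals will be given the cytopathology results (either abnormal, normal, or inadequate/unsatisfactory") by whichever mode of communication they prefer. No date and no safety question are attached to it.

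**The concern.** The plan sets a 30-day SAE window and a by-arm SAE table, but no scheduled step obtains the data for days 1 to 30. A participant who had no event and one who had an event that nobody reported leave the same record.

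At stake is the reading of the most likely result. I.4 says that adverse and serious adverse events are not expected, so the table will probably show zero, or close to it, in both arms. A zero is informative only if it is known how many people it covers. Incomplete reporting can only lower the observed count, and a confidence interval computed on the full sample would not show that loss. The table would describe a new swab used at two insertion depths, as preparation for the parent SOLO study.

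**Working it through.** The documents give no SAE rate, safety margin or precision target, so there is no figure of the plan's own to reproduce. The check has two parts.

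**1. Is any enquiry about SAEs scheduled after the visit?**

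| Place | What it provides | Scheduled SAE question after day 0? |
|---|---|---|
| G.2, adverse event row | A 30-day window, no contact to fill it | No |
| G.2, survey row and footnote | Survey straight after sampling | No (day 0) |
| I.1.1 | Open question permitted | No time point |
| I.3 | Incoming reports only | No |
| F.4 | Result returned to everyone | No safety question, no date |
| Section L | Weekly team review of adverse events, including anxiety about results | No step for obtaining them |

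None does. The table also shows a direct conflict. The adverse event row of G.2 has AEs collected to 30 days after the intervention. I.3 ends AE collection (Grade 3 or higher, related) when the intervention concludes and gives the 30 days to SAEs only.

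**2. What does a zero support?** (illustration)

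Inputs: n = 60 from the protocol summary. The number m whose day-30 status is known is an assumption, because the documents give nothing from which to estimate it.

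With 0 events among m people, the exact one-sided 95% upper limit is 1 − 0.05^(1/m):

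- m = 60: 1 − 0.05^(1/60) = 4.9%
- m = 54: 1 − 0.05^(1/54) = 5.4%
- m = 45: 1 − 0.05^(1/45) = 6.4%
- m = 30: 1 − 0.05^(1/30) = 9.5%

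These limits apply to everyone randomised only if the m people are representative of the rest.

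A second model gives a similar answer. Suppose each SAE reaches staff with probability s (assumed). The limit on the true risk is then the m = 60 limit divided by s. At s = 0.5 this is 4.87% / 0.5 = 9.7%.

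The chance of seeing no reported SAE in 60 people is (1 − p·s)^60. With an assumed true 30-day risk p = 2%:

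- s = 1: 0.98^60 = 30%
- s = 0.5: 0.99^60 = 55%
- s = 0.25: 0.995^60 = 74%

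The less complete the reporting, the more often a clean table appears when the risk is not zero.

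The total need not be 60. Under F.5.3, people who withdraw after randomisation are replaced and their data are used, so the number randomised can be larger.

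**The case against.** The strongest reply is that passive reporting is a proportionate choice and is openly stated. The study is one self-collected swab. Section J records that it was categorised as low risk, and K.6.3 says its procedures closely follow those of the earlier PAC Self-Swab Study. SAEs are not among the four endpoints, and H.2 disclaims power for those endpoints. No SAE threshold exists, so no decision turns on 4.9% versus 9.5%. All of this stands, and it limits the importance of the point. It does not tell the reader of the by-arm table how many people that table covers.

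A reader might also infer several stronger things that the documents do not support:

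- *That nobody is contacted after the visit, or that only events volunteered by participants can be counted.* F.4 has results given to participants, I.1.1 permits a question, and I.3 accepts reports from third parties. What is missing is a scheduled contact to ask.
- *That the plan will report zero out of 60, or test SAEs between arms.* H.3.1 mentions only frequencies in each arm.
- *That reporting will differ between arms.* This is speculation. The kits differ only in the position of the colored mark (F.3), and the reporting instruction in I.3 does not vary by arm.
- *That F.6 ends safety follow-up.* It defines completion by an individual. I.3 still follows known AEs to resolution, withdrawal of consent or loss to follow-up.
- *That anxiety about results is part of the SAE gap.* Such anxiety would not ordinarily be an SAE, and a participant could report it by the routes in I.3.

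**Conclusion.** The point holds in a limited form. The plan commits to 30 days of SAE collection and a by-arm table but schedules no enquiry after day 0. SAE frequency may therefore be under-ascertained, and a zero could not be read as zero among all randomised. This conclusion follows from the text and needs no numerical assumption.

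Its size cannot be derived from the documents. The move from 4.9% (60 known) to 9.5% (30 known) shows scale only and rests on an assumed share. Importance is modest: this is an inexpensive improvement to how safety is ascertained and described, and it does not affect any of the four endpoints. The difference between G.2 and I.3 on the AE window is a plain inconsistency and needs reconciling in any case.

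**What to change.** 1. In I.3 and G.2, add one scripted question about medical events since the swab when the cytology result is returned. If the preferred mode is one-way, put the question in the same message with a means of reply.
2. In I.3 and G.2, add a one-item REDCap message at day 30 asking about hospitalisation or other serious events. The result contact has no fixed date, so it cannot close the window alone.
3. In H.3.1, report by arm: all SAEs from any source, the number randomised (which may exceed 60), and the number with known day-30 status. Do not restrict the count to people who answered. An SAE reported by a hospital or relative about someone not reached must still appear, and people in hospital may be the least likely to reply.
4. If day-30 status is not obtained, label the table *reported SAEs* and attach no rate or confidence limit.
5. In the same amendment, reconcile the AE collection window in G.2 with the one in I.3.

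The cost is a short amendment, one question at a contact that already takes place, one automated item on the platform that already hosts the survey (K.5.1), and staff time to review replies. Email addresses are already confirmed at the consenting session (E.2). Some non-response will remain, and item 3 makes it visible. Item 4 alone needs no new data collection.
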